#### General principles of scoring

The QLQ-C30 is composed of both multi-item scales and single-item measures. These include five functional scales, three symptom scales, a global health status / QoL scale, and six single items. Each of the multi-item scales includes a different set of items - no item occurs in more than one scale. All of the scales and single-item measures range in score from 0 to 100. A high scale score represents a higher response level.

Thus a **high score for a functional scale** represents a *high / healthy level of functioning*, a **high score for the global health status / QoL** represents a *high QoL*, but a **high score for a symptom scale / item** represents a *high level of symptomatology / problems*.

The principle for scoring these scales is the same in all cases:

1. Estimate the average of the items that contribute to the scale; this is the *raw score*.
2. Use a linear transformation to standardise the raw score, so that scores range from 0 to 100; a higher score represents a higher ("better") level of functioning, or a higher ("worse") level of symptoms.

For more details and statistical evaluation, please see: <http://www.eortc.be/home/qol/files/SCManualQLQ-C30.pdf>

## Appendix VI

### Cost Effectiveness

Almost every incremental improvement in survival or progression-free survival comes at a cost. The cost is both financial and experienced in terms of quality of life. Measurement of primary outcomes such as freedom from progression and the most important aspects of human functioning and quality of life will permit a summary equation allowing for differences in quality of life, clinical outcomes, and cost to be incorporated into one equation. This equation is the Quality Adjusted Life Year (QALY) and a study-specific modification, the Quality Adjusted Freedom From Progression Year (QAFFPY). The QALY has been modified in a similar manner for different treatments where survival is not the primary outcome. Much of the work in modifying the QALY began in ophthalmology, where sight-years, not life-years, are the outcome of interest. Examples of modifications to the QALY have included incremental cost per vision-year gained to assess the cost effectiveness of photodynamic therapy with verteporfin for age-related macular degeneration, costs per sight-year saved with screening for diabetic retinopathy, cost-utility analysis for treatments of retinal detachment associated with severe proliferative vitreoretinopathy, and the cost-utility of cataract surgery. However, the QALY has been used in other studies where survival is not the primary outcome of interest, such as the costeffectiveness of memantine in the treatment of patients with moderately severe to severe cognitive impairment from Alzheimer's and cochlear implantation for patients unable to gain effective speech recognition with hearing aids. We will model costs using Medicare reimbursement and measure utilities with the brief five-item EuroQol (EQ-5D).

The EQ-5D is a method for obtaining valuations (utilities) of health-related quality of life (HRQOL) to be used as an adjustment to survival and in the cost-utility analysis. Developed in 1987, the EQ-5D is used by investigators and the pharmaceutical industry throughout the United States, Europe, and Asia. It is one of only several measures recommended for use in cost-effectiveness analyses by the Washington Panel on Cost Effectiveness in Health and Medicine. The EQ-5D instrument is intended to complement other forms of QOL measures, and it has been purposefully developed to generate a generic cardinal index of health, thus giving it considerable potential for use in economic evaluation. The argument by some that a generic measure does not capture some of the disease- or treatment-specific concerns of a given study misses the point. This cost-effectiveness analysis is being done for purposes of exploring the means to inform macro (health policy, payer) decision making, not micro (individual) decision making. The findings from the disease-specific QOL instruments and treatment-related side effect QOL instruments described above will help inform individual decision making. The role of the EQ-5D is to measure HRQOL at a macro level, in the same metric as it has been measured across numerous diseases, including cancer.

This instrument gives us the ability to compare across and within diseases the "big picture" of what the experts who developed the EQ-5D considered the primary health states of interest to humans: mobility, self care, usual activities, pain/discomfort, and anxiety/depression. Further, there is no standardized measure to assess and compare disease-specific utilities across or within diseases. Unlike the EQ-5D, the actual content of standard gamble (SG) and time tradeoff (TTO) methods vary widely among studies and are subject to wide variations in amount and type of information presented, message framing, and visual aids, making replication of utilities with the SG or TTO extremely difficult. Therefore, using the EQ-5D, an exploratory aim is to evaluate the cost-utility of the treatment arm demonstrating the most significant benefit (in terms of the primary outcome), in comparison to other widely accepted cancer and non-cancer therapies. We will also assess cost-utility among the arms to assess which therapy dominates. We will assess the value added of the summary score known as a Quality Adjusted Life Year (QALY), and for this study the Quality Adjusted FFP Year, that combines benefits of duration of freedom from progression (FFP) and decrements of quality of life with financial cost of increasingly aggressive and costly therapy.

The EQ-5D has been used across numerous disease sites, including cancer. For example, the EQ-5D mean score for 95 patients with NSCLC (93% male, mean age 62 years) was 0.58 (SD 0.32) as measured by the questionnaire and 0.58 (SD 0.20) as measured by the visual analogue scale (VAS) version. The EQ-5D has been used to assess QALYs and the economic value of prostate cancer screening, and treatment of pain related to prostate cancer metastasis. Further, the EQ-5D was used in a recent study to estimate the

economic value of the welfare loss due to prostate cancer pain by estimating the extent to which pain affects health-related quality of life among patients with prostate cancer. Health status and economic outcomes were modeled among a well-defined population of 200,000 Swedish prostate cancer patients. Health utility ratings (using the EQ-5D) were obtained from a subset of 1,156 of the prostate cancer patients. A descriptive model showed that optimal treatment that would reduce pain to zero during the whole episode of disease would add on average 0.85 quality-adjusted life years (QALY) to every man with prostate cancer; the economic value of this welfare loss due to prostate cancer pain was approximately \$121,240,000 per year.

#### Quality-Adjusted Survival and Freedom from Progression

Quality-adjusted survival and freedom from progression can be defined in the same manner, by the weighted sum of different time episodes added up to a total quality-adjusted life-year or freedom from progression-year [ $U = \sum \text{sum of quality (qi) of health states K times the duration (si) spent in each health state}$ ].

#### Cost-Effectiveness and Cost-Utility

Cost-utility will be analyzed for planned publication at two time points: 1) at 1 year post-therapy, looking at initial treatment costs and quality of life and 2) at five years post-therapy. The cost-utility analysis will be done after the primary endpoint results are published.

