### **9.1.6 Evaluation of Cost-Utility**

9.1.6.1 Evaluation the cost-utility of the treatment arm (in terms of the primary outcome) in comparison with other widely accepted cancer and non-cancer therapies will be assessed by using the brief five-item EuroQol group EQ-5D-3L. Assessments will take place prior to treatment and then every six months for the first year and then yearly afterwards.

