11.3 Sample Size

11.3.1 **Overview:** The primary goal of this study is to monitor shrinkage in adenoma size and volume following treatment.

11.3.2 **Sample Size Derivation:** The predicted partial or complete response rate (PR+CR) of treated subjects at a follow-up interval of 12 months is the determinant of sample size. A PR + CR rate of 10% or less would be considered insufficiently low for further investigation of this treatment, whereas a PR + CR probability of 50% or higher will be considered worthy of future investigation. If the true PR + CR rate is 50%, a sample size of 10 patients will provide 87% power to detect a significantly higher RTS than 10% with an alpha level of 0.025. To assure an adequate number of evaluable patients, allowing for a small number of patients who would be lost to follow-up or otherwise found non evaluable, a total of up to 12 patients will be enrolled. This analysis applies to both cohorts (those with and without previous radiation therapy)

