11.5 Analysis Plan

11.5.1 Interim Reports

11.5.1.1 Interim reports will be updated at least every six months until the results of the study are published. In general, the interim reports will contain information about patient accrual rate with projected completion dates of the trial, status of QA review and compliance rate of treatment per protocol, and the frequencies and severity of toxicity.

11.5.1.2 *The Analysis of Tumor Shrinkage:* This analysis will be carried out when each patient has had at least 730 days (i.e., 24 months) of follow-up. The percent change in size and volume of the adenoma will then be calculated by subtracting the post-treatment measurements from the pre-treatment measurements then divided by the pre-treatment measurements and then multiplied by 100. The mean, median and standard deviation of the percent change will be determined.

11.5.1.3 *Estimation of Secondary Endpoints Related to the Efficacy:* Cumulative incidence approach will be used to estimate the progression free survival. For any individual patient, progressive disease (PD) within the treated lesion will be scored as PD for that patient

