#### Measurement of Costs

Direct medical costs fall into three categories: 1) initial therapy costs; 2) costs of managing the most common side effects as determined by this study; and 3) costs of managing recurrence. Costs for interstitial radiotherapy will be determined using CPT coding and Medicare reimbursement rates. Costs of common management strategies of the most common side effects documented in this study (e.g., Imodium® for diarrhea) will be estimated from regional costs per unit. Costs for managing recurrence will assume the following salvage therapies: hormone therapy and chemotherapy. Costs will include professional fees, cost/inpatient day, drugs, and supplies. Direct non-medical costs such as the cost of work lost or of transportation will not be measured. Incremental differences in costs and outcomes will be compared for the different alternatives and for the dominant alternative to other established therapies documented in the literature.

The EQ-5D is a two-part self-assessment questionnaire. The first part consists of 5 items covering 5 dimensions (mobility, self care, usual activities, pain/discomfort, and anxiety/depression). Each dimension is measured by a three point Likert scale (1-no problems, 2-moderate problems, and 3-extreme problems). There are 243 (=35) health states. The second part is a visual analog scale (VAS) valuing the current health state measured by 100 point scale with 10 point interval (0-worst imaginable health state, 100-best imaginable health state).

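### The 1-year cost-utility analysis is described with initial treatment costs alone, although Appendix VI defines three categories of direct medical cost

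*Combined protocol and SAP*

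**What the plan says.** Objective 2.2.5 sets a cost-utility comparison with other accepted therapies. Appendix VI gives the detail.

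- **Time points.** Under Cost-Effectiveness and Cost-Utility, results are planned for publication "at 1 year post-therapy, looking at initial treatment costs and quality of life and 2) at five years post-therapy". A cost scope is attached to the first time point and none to the second.
- **Cost categories.** Under Measurement of Costs: "Direct medical costs fall into three categories: 1) initial therapy costs; 2) costs of managing the most common side effects", followed by "3) costs of managing recurrence". No category is tied to a time point.
- **Utilities.** Section 9.1.6 sets the EQ-5D schedule: "Assessments will take place prior to treatment and then every six months for the first year and then yearly afterwards".
- **Quality-adjusted time.** Under Quality-Adjusted Survival and Freedom from Progression, the total is defined "by the weighted sum of different time episodes added up to a total quality-adjusted life-year or freedom from progression-year". Nothing is said about patients whose follow-up is incomplete.
- **Progression-free survival.** Section 11.5.1.3 says: "Cumulative incidence approach will be used to estimate the progression free survival". This is not linked to the quality-adjusted total.

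**The concern.** A cost-utility ratio should count costs and health effects over the same period and from the same events. Here the 1-year cost side names one of the three categories, while the quality-of-life side has no matching restriction. Care given in year 1 for a side effect or recurrence would add no cost, even though the event may lower the 6- or 12-month EQ-5D.

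The protocol itself foresees such care. Appendix VII lists bleeding, leakage of cerebrospinal fluid and neurological deficits as risks of seed placement. Section 6.8.2 foresees that a migrated seed may have to be moved or taken out. Section 6.8.3 foresees treatment for suspected radiation necrosis. None of these places says how much would fall within 12 months.

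At stake is a published 1-year figure on a narrower cost basis than the appendix's own definition, set beside therapies whose cost scope may differ. A smaller question concerns the 5-year total: a patient lost before year 5 has an unobserved duration, and the plan does not say how that patient enters the sum.

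**Working it through.** The plan states no costs, utilities or loss rates for this analysis, so there is no figure of its own to reproduce. The sizes below rest on labelled assumptions.

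**1. First-year cost.** Take the initial treatment cost per patient as 1. Let *p* be the share of patients who need side-effect or recurrence care in year 1, and *f* its cost per affected patient relative to the initial treatment. True mean cost is 1 + *pf*, and the cost counted is 1. The understatement as a share of true cost is *pf*/(1 + *pf*). The 12 is the maximum enrolment per cohort (11.3.2); *p* and *f* are assumed.

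| Patients affected | *f* | *pf* | Understatement |
|---|---|---|---|
| 0 of 12 | any | 0 | 0% |
| 1 of 12 | 0.5 | 1/24 | 1/25 = 4.0% |
| 1 of 12 | 1.0 | 1/12 | 1/13 = 7.7% |
| 2 of 12 | 0.5 | 1/12 | 1/13 = 7.7% |
| 2 of 12 | 1.0 | 1/6 | 1/7 = 14.3% |

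This takes the care to fall within the second or third category. The second covers only the most common side effects, so care for a rare complication could remain unpriced even after the fix.

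**2. What the EQ-5D can register.** Readings fall at 0, 6 and 12 months (9.1.6). With straight-line interpolation (an assumption; the plan gives no rule) they carry weights of 3, 6 and 3 months. For a fixed drop in utility:

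- months 1 to 4: no reading affected, 0 of 3 months captured (0%);
- months 5 to 7: the 6-month reading is affected, 6 months counted against 2 true (300%);
- months 1 to 12: the 6- and 12-month readings are affected, 6 + 3 = 9 counted against 11 true (82%).

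So first-year harm can enter the utility side, but it does so unevenly.

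**3. The 5-year total, if observed time were simply summed.** Suppose utility is constant, 2 of 12 patients are lost at year *t*, and all 12 would otherwise have stayed alive (for the QALY) or progression-free (for the QAFFPY) to year 5. The change relative to the true total is (10 × 5 + 2*t*)/(12 × 5) − 1:

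- *t* = 1: 52/60 − 1 = −13.3%;
- *t* = 2: 54/60 − 1 = −10.0%;
- *t* = 3: 56/60 − 1 = −6.7%.

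With complete follow-up the change is 0%.

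**The case against.** The strongest defence is that the plan never says *only*. The 1-year report is openly labelled as looking at one kind of cost, and Measurement of Costs lists all three categories without tying any to a date, so an analyst could include them all at both points. This lowers the severity but does not remove the mismatch. The qualifier is attached to year 1 alone, and initial therapy is listed separately from side effects and recurrence, so the plain reading is a restriction.

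Four stronger readings are tempting, and the documents do not support them.

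- **That the EQ-5D captures all first-year harm.** A complication that arises and resolves between readings never reaches it and may be absent from both sides.
- **That the 1-year ratio is always too favourable.** Cost is understated only if side-effect or recurrence care occurs in year 1. How the ratio looks beside other therapies also depends on which costs those comparators count, and the documents do not say.
- **That the 5-year total is biased by construction.** The weighted sum defines a quantity; it does not tell the analyst to add up observed time. The defect is an unstated method. Even a literal sum loses nothing with complete follow-up, and for the QAFFPY nothing from a patient lost after progression.
- **That the sample-size section predicts 5-year loss.** The allowance in 11.3.2, "allowing for a small number of patients who would be lost to follow-up or otherwise found non evaluable", concerns evaluability for the 12-month response. Section 3.3.4 asks that patients be available for the whole study, and 10.1.2 schedules quality-of-life follow-up to year 10.

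It is also fair that the aim is called exploratory in Appendix VI, follows publication of the primary results and has no decision rule.

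**Conclusion.** The point holds for the 1-year cost scope. As written, the analysis leaves out two of the appendix's three cost categories, and first-year cost is understated whenever such care occurs. The size is 4% to 14% if 1 to 2 of 12 patients need care costing 0.5 to 1.0 times the initial treatment, and 0% if none do. Those rates and costs are assumptions. The direction of the error in cost is known; its size is not.

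The 5-year point is secondary: handling of incomplete follow-up is missing. The shortfall of 7% to 13% would arise only if observed time were summed literally and 2 of 12 patients were lost between years 1 and 3 while still alive or progression-free.

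Severity is minor. Cost-utility is a secondary objective in 2.2.5 and exploratory in Appendix VI, the trial has one arm and at most 24 patients, and the primary endpoint is unaffected.

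**What to change.** 1. In Appendix VI, Cost-Effectiveness and Cost-Utility, state that both analyses count all three categories under Measurement of Costs, incurred up to the horizon (12 months and 5 years).
2. In Appendix VI, Quality-Adjusted Survival and Freedom from Progression, state that mean quality-adjusted time to each horizon is the area under the survival curve (QALY) or the freedom-from-progression curve (QAFFPY), weighted by mean EQ-5D in each interval, with bootstrap intervals over patients.
3. Reconcile the second change with the cumulative incidence approach in 11.5.1.3: say which curve feeds the QAFFPY and how death enters it.

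The cost is a few sentences and a little more analysis. The assessments already scheduled can supply the utilities. If first-year side-effect or recurrence care occurs, the 1-year ratio becomes slightly less favourable.

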#### Measurement of Costs

Direct medical costs fall into three categories: 1) initial therapy costs; 2) costs of managing the most common side effects as determined by this study; and 3) costs of managing recurrence. Costs for interstitial radiotherapy will be determined using CPT coding and Medicare reimbursement rates. Costs of common management strategies of the most common side effects documented in this study (e.g., Imodium® for diarrhea) will be estimated from regional costs per unit. Costs for managing recurrence will assume the following salvage therapies: hormone therapy and chemotherapy. Costs will include professional fees, cost/inpatient day, drugs, and supplies. Direct non-medical costs such as the cost of work lost or of transportation will not be measured. Incremental differences in costs and outcomes will be compared for the different alternatives and for the dominant alternative to other established therapies documented in the literature.

The EQ-5D is a two-part self-assessment questionnaire. The first part consists of 5 items covering 5 dimensions (mobility, self care, usual activities, pain/discomfort, and anxiety/depression). Each dimension is measured by a three point Likert scale (1-no problems, 2-moderate problems, and 3-extreme problems). There are 243 (=35) health states. The second part is a visual analog scale (VAS) valuing the current health state measured by 100 point scale with 10 point interval (0-worst imaginable health state, 100-best imaginable health state).

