### 6.8.2 Seed Migration

6.8.2.1 Follow up imaging on the scheduled intervals listed below (9.1.1) will be used to monitor the position of the implanted radioactive seeds. There is the potential for the seeds to migrate and/or change position in response to shrinkage of the tumor secondary to treatment. This change in location of the seeds could potentially cause an increased dose to OARs. If this occurs, then measures should be attempted to move or remove the seed which has migrated if the treating physician determines appropriate. Seeds that are removed will be handled and disposed of as per institutional policy

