**The sample size of this study will not exceed 24 patients.**

11.3.3 There will be an early stopping rule for unexpected toxicity. If at any point during the study more than 1/6 of patients treated to date experience study treatment-related grade 4-5 toxicity of any kind, study enrollment will be suspended. Treatment related events include those related or possibly related to therapy.

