## Appendix VII

### Risks to Subjects

| Procedure  | Risks   | Measures to Minimize Risks   |
|---|--|---|
| History and physical exam (H&P)                             | Discovery of previously unknown condition  | Will be performed by MD and/or nurse practitioner with oncology experience.   |
| MR imaging / CT imaging of the brain                        | Discovery of previously unknown condition/recurrence or progression of pituitary adenoma; discomfort           | Will be performed by nurse/technician with radiology experience   |
| Blood draws (at all study timepoints)                       | Discomfort, bleeding, bruising, dizziness, fainting, infection   | Blood will be drawn by an experienced phlebotomist.   |
| Zubrod Performance status evaluation                        | Discomfort, psychological stress of answering personal questions   | Subjects informed that they may refuse to answer, take a break, or discontinue participation at any time  |
| Neurocognitive evaluation                                   | Discomfort, psychological stress of answering personal questions   | Subjects informed that they may refuse to answer, take a break, or discontinue participation at any time  |
| QOL assessment  | Discomfort, psychological stress of answering personal questions   | Subjects informed that they may refuse to answer, take a break, or discontinue participation at any time  |
| Interstitial seed placement                                 | Hemorrhage, cerebral spinal fluid leak, neurological deficits

Constitutional:
likely: fatigue | Participants will be educated and asked to inform study personnel if encounter symptoms.  |
| FAX transmittal of case report forms (CRFs) to primary site | Loss of privacy  | Sensitive patient information will be blacked-out. CRFs will only be identified by subject initials and unique, study identification number before fax transmittal. |
| Unforeseen risks  | E.g., unpredictable interaction between radiotherapy and concomitant medications                               | Strong encouragement to report any difficulties and keep researchers aware of any change in medications   |

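### The cost rule counts only the most common side effects, so an uncommon severe event or a later seed removal need not be costed; scheduled follow-up MRI has no cost category

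*Combined protocol and SAP*

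**What the plan says.** The rule is in Appendix VI, Measurement of Costs. The list opens with "Direct medical costs fall into three categories: 1) initial therapy costs", continues with "costs of managing the most common side effects as determined by this study", and ends with the cost of managing recurrence. The method for each category follows:

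- Initial therapy: "Costs for interstitial radiotherapy will be determined using CPT coding and Medicare reimbursement rates".
- Side effects: "Costs of common management strategies of the most common side effects documented in this study" are to be estimated from regional unit costs. This repeats the frequency limit. The example given is an antidiarrhoeal drug.
- Recurrence: "Costs for managing recurrence will assume the following salvage therapies: hormone therapy and chemotherapy".

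The resources named are professional fees, inpatient days, drugs and supplies. Only non-medical costs are excluded by name. The opening text of Appendix VI says costs will be modelled on Medicare reimbursement.

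Other sections describe harms and procedures that the cost rule has to deal with:

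- Appendix VII lists "Hemorrhage, cerebral spinal fluid leak, neurological deficits" as risks of seed placement, with no frequencies. Fatigue is the only one marked likely.
- Section 6.8.2 says that, if a seed shifts and could raise the dose to nearby organs, "measures should be attempted to move or remove the seed which has migrated", if the treating physician judges this appropriate. Section 3.3.2 treats removal as rare.
- Section 9.1.1.2 schedules serial MRI, and Appendix VI plans cost-utility analyses at one and five years.

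**The concern.** For a permanent intracranial implant, the events likely to be expensive are not necessarily the frequent ones. A rule that selects events by frequency alone can price fatigue and leave out a late haemorrhage or a second procedure on a seed. The two sides of the cost-utility ratio are then treated unequally. EQ-5D is collected before treatment, every six months in the first year and yearly afterwards (9.1.6.1), so a lasting severe harm lowers the quality-adjusted time while the cost of treating it may be missing. The trial is single-arm and sets its costs against therapies reported in the literature, so nobody can assume that the same omission was made on the other side. Because no threshold is given, someone would also have to decide which events count as common after seeing the data.

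**Working it through.** The plan states no figure on this point, so there is none to reproduce. The check sets the cost rule against the foreseen events, then counts what can be counted.

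**1. Does each item have a cost category?**

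| Item | Foreseen in | Category in Measurement of Costs |
|---|---|---|
| Severe event during the implant admission | Appendix VII; 6.6.1 (CT the same or next day, also used to look for bleeding) | Possibly initial therapy, through inpatient days; the text does not say |
| Later severe event that proves uncommon | Appendix VII; 9.1.3.1 | None assured |
| Later move or removal of a seed | 6.8.2; called rare in 3.3.2 | None assured |
| Scheduled follow-up MRI | 9.1.1.2; Appendix I | None |

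The second and third rows follow from the limit to the most common side effects. The fourth does not: MRI is not a side effect, and it is missing because none of the three categories covers surveillance.

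**2. Could an event happen and still be uncommon?** The documents give no rates, so these are assumptions. With N = 24, the maximum sample size, and rate p per patient, the expected number is 24p and the chance of at least one event is 1 − (1 − p)^24.

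- p = 2%: expected 0.48; chance 1 − 0.98^24 = 38%.
- p = 5%: expected 1.2; chance 1 − 0.95^24 = 71%.
- p = 10%: expected 2.4; chance 1 − 0.90^24 = 92%.

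Over this range a given type of event may well occur, yet typically only in none to a few patients. Whether that ranks among the most common is left open.

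**3. Does the toxicity rule limit the problem?** Section 11.3.3 suspends enrolment if "more than 1/6 of patients treated to date experience study treatment-related grade 4-5 toxicity". At full enrolment 24 × 1/6 = 4, and four is not more than 1/6, so four such patients would not trigger it. The rule acts on enrolment only, so four is not a ceiling on later events.

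**4. Size.** With n unpriced events at average cost c, the understatement of mean cost per patient is n × c / 24. It cannot be negative. The documents supply neither n nor c, so no amount or percentage follows.

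**5. MRI count to month 60.**

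- Section 9.1.1.2 and Appendix I: 8 (months 3 to 24) + 4 (months 30 to 48) + 1 (month 60) = 13 per patient; 13 × 24 = 312 scans with complete follow-up.
- Section 10.1.2, which collects adenoma measurements six-monthly after month 12: 4 (months 3 to 12) + 6 (months 18 to 48) + 1 (month 60) = 11 per patient; 11 × 24 = 264.
- Both schedules give 4 per patient by one year.

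**The case against.** The best defence is that the rule is loose rather than exclusionary. The most common side effects are to be determined by the study itself, and in at most 24 patients a few events of one type could qualify. Inpatient days are among the resources to be costed, which fits poorly with a plan that prices only mild events. Only seed removal is called rare. Appendix VII gives no frequency for haemorrhage, cerebrospinal fluid leak or neurological deficit, and several serious toxicities are monitored by name in 9.1.3.1. A bleed found on the post-implant CT could fall under initial therapy. Section 6.2.2.1 describes MRI frequency as standard of care, so its cost may cancel against patients followed in the same way. Appendix VI calls the analysis exploratory.

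Much of this stands, and it rules out two stronger readings. A reader might infer that severe events are priced at zero and express the loss as a share of the initial procedure cost. The documents do not support that. The undefined limit leaves room for a severe event that recurs, and any percentage would need a cost ratio that appears nowhere. The more severe events one supposes, the likelier it is that a single type would rank as common and be priced. A reader might also infer that the MRI gap biases the comparison downward. That depends on whether the comparator costs include imaging, which the plan does not say.

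The defence does not show any text that assures a cost for a late, uncommon severe event or a late seed procedure. Nor does the plan offer standard of care as its reason for leaving imaging out.

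**Conclusion.** The point holds as a gap in the costing rule. Under its present wording, an uncommon treatment-related severe event, or a later procedure to move or remove a seed, need not be costed while its effect on utility can be counted. The omission can only lower the implant's own cost. The amount is unknown: it depends on event rates, on unit costs, and on how much of an early event is absorbed into initial therapy, and the documents give none of these. Scheduled MRI is a separate gap of 13 or 11 scans per patient to month 60. It matters for the comparison only if the comparator costs treat imaging differently.

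The stakes are small. Objective 2.2.5 alone is affected. The primary endpoint, the sample size and the safety monitoring are untouched.

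**What to change.** 1. In both places in Appendix VI, Measurement of Costs, replace the limit to the most common side effects with: *all treatment-related (possibly, probably or definitely) grade 3-5 adverse events and every procedure to move or remove a seed, whatever their frequency, plus the most common lower-grade side effects*. The undefined term then governs lower-grade events only.
2. Reconcile the price source. Measurement of Costs uses regional unit costs for side effects, whereas the opening of Appendix VI says Medicare reimbursement. Name one, or say which applies to which item.
3. Include scheduled follow-up MRI in the five-year cost, or exclude it only if the comparator costs also exclude it. State which schedule is counted, since 9.1.1.2 and 10.1.2 differ.

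Grade and attribution are already recorded (6.9.3 and 9.2.1), so the events can be identified. Section 10.1.2 has no resource-use item, so some extraction from source records is needed. The other cost is a higher, less favourable figure for the implant. The cost-utility analysis follows publication of the primary endpoint, so the wording can be settled before costing starts.
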